 - Other genomic profile with mechanistic rationale as agreed upon by the Investigator and Sponsor

Note: For all participants, an anonymized/redacted Molecular Pathology report should be submitted to the Sponsor or designee during Pre-screening to confirm eligibility. For details, see the Molecular Eligibility Manual.

- 11. Acceptable organ function at Screening, as evidenced by the following laboratory data:
 - a. Creatinine clearance ≥ 60 mL/min using Cockcroft-Gault equation or institution standard formula.
 - *US only:* For participants 12 to 17 years of age, adequate renal function is defined as: calculated creatinine clearance by Cockcroft- Gault or institutional standard, including institutional formula specific for this age group.
 - b. Total bilirubin \leq 1.5 × upper limit of normal (ULN) or < 3.0 × ULN if known Gilbert's disease.
 - c. Aspartate aminotransferase (AST) and alanine aminotransferase (ALT) \leq 3.0 \times ULN or \leq 5.0 \times ULN in the case of presence of liver metastases.
 - d. Albumin > 2.0 g/dL

- 12. Acceptable hematologic function at Screening:
 - a. No red blood cell (RBC) or platelet transfusions, and no myeloid, erythroid, or thrombopoietic growth factors within 7 days of the first dose of trial intervention
 - b. Hemoglobin \geq 9.5 g/dL except for participants with neuroblastoma with bone marrow involvement who are required to have hemoglobin \geq 8.0 g/dL
 - c. Absolute neutrophil count (ANC) \geq 2000 cells/mm³ except for participants with neuroblastoma with bone marrow involvement who are required to have ANC \geq 1000 cells/mm³. Participants with neuroblastoma with bone marrow involvement are required to have ANC \geq 750/uL.
 - d. Platelet count ≥ 100,000 cells/mm³. Participants with neuroblastoma without bone marrow involvement are required to have platelet count ≥ 100,000 cells/mm³ (transfusion independent, defined as not receiving platelet transfusions for at least 7 days prior to enrollment). Participants with neuroblastoma with bone marrow involvement are required to have platelet count ≥ 75,000 cells/mm³ (transfusion independent, defined as not receiving platelet transfusions for at least 7 days prior to enrollment).
- 13. Negative pregnancy test (serum) for women of childbearing potential (WOCBP) at Screening.

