12.1 Dose Limiting Toxicities

The number of DLTs will be summarized by treatment arms for the DLT Evaluable Population. A toxicity will be considered a DLT if it occurs from the first dose to the end of Cycle 1 (including the PK evaluation period), meets the pre-defined criteria for DLTs, is deemed at least possibly related to trial treatment, and is not clearly and incontrovertibly due to disease progression or extraneous cause. Toxicity will be assessed using CTCAE v 5.0, unless other specified. Details of DLTs will be listed.

DLTs will be defined as any of the following:

Any death not clearly due to the underlying disease or extraneous causes

Hematologic TEAES:

- Grade 4 neutropenia
- Febrile neutropenia (defined as absolute neutrophil count (ANC) <1000 cells/ μ L with a single temperature of 38.3°C [100.4°F] for > 1 hour).
- Grade 4 thrombocytopenia or Grade 3 thrombocytopenia associated with Grade \geq 2 bleeding.
- Grade 4 anemia or Grade 3 anemia requiring red blood cell (RBC) transfusion given to participants with documented anemia-related symptoms.

Non-Hematologic TEAEs:

- Any Grade \geq 3 TEAE except the below
 - 1. Grade ≥ 3 non-hematologic laboratory abnormalities that are asymptomatic and respond to medical intervention or resolve to grade 1 in \leq 72 hours.
 - 2. Grade 3 fatigue with duration < 7 days
 - 3. Grade \geq 3 nausea/vomiting/diarrhea that lasts \leq 72 hours and resolves with or without optimal supportive care.
 - 4. Grade \geq 3 amylase or lipase elevation not associated with symptoms or clinical manifestations of pancreatitis.
 - 5. The use of red blood cell transfusion for anemia Grade <3 or the use of G-CSF for Grade <4 neutropenia
- Symptomatic Grade ≥ 3 QTc prolongation (QTcF ≥ 501 msec on at least two separate electrocardiogram (ECGs)), or asymptomatic Grade ≥ 3 QTc prolongation that has been confirmed by repeat testing and reevaluation by a qualified person and persists after correction of reversible causes such as electrolyte abnormalities or hypoxia.
- Drug-induced liver injury meeting Hy's Law criteria defined as:
 - 1. ALT or AST ≥3-fold above the Upper Limit of Normal (ULN) or 5.0 x ULN in the case of liver metastases at baseline and
 - 2. Serum total bilirubin \geq 2-folde above ULN (without findings of cholestasis) and
 - 3. Alkaline phosphatase $\leq 2 \times ULN$ and
 - 4. No other overt reason for liver injury

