12.3 Clinical Laboratory Tests

Selected hematology and serum chemistry parameters including Alanine Aminotransferase (ALT), Aspartate Aminotransferase (AST), Creatinine, Total Bilirubin, Hemoglobin, Neutrophiles and Platelets Count will be summarized for Safety population. All other laboratory results, including pregnancy test results, will be listed only.

For all quantitative parameters, the actual value and the change from baseline by scheduled time of evaluation will be summarized by dose levels and dose schedule for each study visit using descriptive statistics. Both scheduled and unscheduled visits will be considered for baseline derivation.

Laboratory parameters are also graded according to CTCAE v5.0 for the selected parameters listed above. A shift table, presenting the 2-way frequency tabulation for baseline and the worst post-treatment value according to the NCI-CTCAE grade, will be provided. Laboratory parameters with CTCAE grading in both high and low directions will be summarized separately. Both scheduled and unscheduled post-treatment visits will be considered in tabulation of the worst post-treatment value. Additionally, the number and percentage of participants with the following potentially clinically significant abnormal liver function test will be presented:

- ALT >3xULN, \geq 5xULN, \geq 10xULN, and \geq 20xULN
- AST >3xULN, \geq 5xULN, \geq 10xULN, and \geq 20xULN
- Total bilirubin >2xULN

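### SAP 12.3 counts ALT or AST >3×ULN and bilirubin >2×ULN with no baseline condition, although criterion 11b-c admits participants already above these cut-offs; the Hy's Law bilirubin component overlaps with criterion 11b as well

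*Protocol*

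**What the plan says.** **Entry (Protocol 1.1, inclusion criterion 11b-c).** Total bilirubin must be at most 1.5×ULN, or "< 3.0 × ULN if known Gilbert's disease". ALT and AST must be at most 3.0×ULN, or at most 5.0 times "ULN in the case of presence of liver metastases".

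**Liver table (SAP 12.3).** The SAP states that "the number and percentage of participants with the following potentially clinically significant abnormal liver function test will be presented". Nine rows follow: ALT at >3, ≥5, ≥10 and ≥20×ULN, AST at the same four levels, and "Total bilirubin >2xULN". No row refers to the baseline value. The same section also plans change from baseline by visit and a shift table of baseline against worst post-treatment CTCAE grade.

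**Hy's Law DLT (SAP 12.1).** Four components must hold together:
- ALT or AST at least 3-fold, "or 5.0 x ULN in the case of liver metastases at baseline and"
- total bilirubin at least "2-folde above ULN (without findings of cholestasis) and"
- alkaline phosphatase at most 2×ULN
- "No other overt reason for liver injury"

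Every DLT must also be judged at least possibly related to treatment and not clearly due to progression or an extraneous cause.

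**Comparison (SAP 12.5).** For the absolute QTcF categories, the denominator is limited to participants with a normal baseline and at least one later assessment.

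**The concern.** A table of threshold exceedances is read as a picture of what happened on treatment. If the entry criteria admit people who already exceed the threshold, part of the count reflects their disease or their Gilbert's rather than RP-1664. SAP 7 presents tables by dose level and schedule, where columns may hold only a few participants, so one such person can change how a column looks.

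The Hy's Law definition raises a related question. Its ALT/AST component was adapted to the liver-metastasis allowance at entry. Its bilirubin component was not adapted to the Gilbert's allowance. Dose decisions may rest on as few as two DLT-evaluable participants (Protocol 1.1; SAP 4.1), so it should be clear beforehand how a bilirubin that was already raised at entry is treated.

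**Working it through.** The documents give no figure to reproduce. The check compares each entry range with each cut-off, in multiples of ULN.

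| Test and group | Allowed at entry | Cut-off | Overlap |
|---|---|---|---|
| Bilirubin, known Gilbert's | <3.0 | SAP 12.3: >2 | >2.0 to <3.0 |
| Bilirubin, known Gilbert's | <3.0 | Hy's Law: ≥2 | 2.0 to <3.0 |
| Bilirubin, others | ≤1.5 | either | none |
| ALT/AST, liver metastases | ≤5.0 | SAP 12.3: >3 | >3.0 to 5.0 |
| ALT/AST, liver metastases | ≤5.0 | SAP 12.3: ≥5 | exactly 5.0 only |
| ALT/AST, any | ≤5.0 | SAP 12.3: ≥10, ≥20 | none |
| ALT/AST, liver metastases | ≤5.0 | Hy's Law: 5.0 | exactly 5.0 if read as ≥; none if read as > |
| ALT/AST, no liver metastases | ≤3.0 | SAP 12.3: >3 | none |
| ALT/AST, no liver metastases | ≤3.0 | Hy's Law: ≥3 | exactly 3.0 only |

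**SAP 12.3.** Three of the nine rows overlap over a real range: ALT >3, AST >3 and bilirubin >2. Two rows (ALT ≥5, AST ≥5) touch at a single value. Four rows (≥10 and ≥20 for each enzyme) cannot overlap.

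**Hy's Law.** Without Gilbert's, a participant at the entry limit needs bilirubin to rise by 2.0/1.5 − 1 = 33% to meet the bilirubin component. With Gilbert's and an entry value of 2.0 to <3.0, no rise is needed. For that participant the ALT/AST, alkaline phosphatase, other-cause and relatedness conditions decide the case.

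**Size.** The documents do not give the share of participants above a cut-off at entry. Call it p, as an assumption. The expected number among the planned 80 is 80p, and the chance of at least one in a cohort of 3 is 1 − (1 − p)³.

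| Assumed p | Expected of 80 | At least one in a cohort of 3 |
|---|---|---|
| 1% | 0.8 | 1 − 0.99³ = 3.0% |
| 5% | 4 | 1 − 0.95³ = 14.3% |
| 10% | 8 | 1 − 0.90³ = 27.1% |

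These figures describe participants who could be counted in a SAP 12.3 row with no change on treatment. They are not probabilities of a DLT.

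**The case against.** The case against has several sound parts.

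- **Baseline is not ignored in SAP 12.3.** The shift table and the change-from-baseline summaries show who entered with abnormal values. That is true, but those outputs stand beside the threshold counts and do not correct them.
- **The primary endpoint is not inflated.** A reader might infer that it is. SAP 12.2 defines a TEAE as an event absent before treatment or one that worsens, so an unchanged entry value is not a TEAE. The affected counts are supplementary and descriptive.
- **ALT/AST entry values do not pre-fill the Hy's Law definition.** This reading is tempting because criterion 11c goes up to 5.0×ULN. SAP 12.1 already uses 5.0×ULN for liver metastases at baseline, so contact is at the boundary value only.
- **A raised entry bilirubin is not itself a DLT.** All four components and the relatedness test must be met. These safeguards rest on judgement, and SAP 12.1 does not say how known Gilbert's enters that judgement, so they reduce the problem without settling it.
- **One DLT among two or three evaluable participants is a rate of 50% or 33%.** That would be a large effect, but the figure assumes that the DLT has already occurred. The documents give no basis for the probability of the whole chain.

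There is also a point of wording. Read literally, two-fold above ULN could mean 3×ULN, which would remove the Hy's Law overlap. SAP 12.3 uses >2×ULN for bilirubin, which makes that reading less likely.

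**Conclusion.** The point holds for three rows of SAP 12.3 and, separately, for one component of the Hy's Law DLT.

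As written, the ALT >3×ULN, AST >3×ULN and bilirubin >2×ULN rows count eligible participants whose values were above the cut-off before the first dose and never moved. SAP 12.3 does not expressly limit these rows to post-treatment values; the preceding sentence suggests it. The overlap exists either way. Its existence follows from the stated limits alone, while its frequency is unknown.

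For Hy's Law, a Gilbert's participant entering at 2.0 to <3.0×ULN already meets the bilirubin component, taking the threshold as 2×ULN. The SAP has no provision matching criterion 11b, although it has one matching criterion 11c. The documents do not support the further claim that such a participant would be declared a DLT.

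This is an inexpensive improvement to the safety tables and a cross-reference to settle. It does not threaten the primary analysis.

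**What to change.** **SAP 12.3.** For the ALT >3×ULN, AST >3×ULN and total bilirubin >2×ULN rows, count newly occurring post-treatment values among participants at or below that cut-off at baseline. Apply the restriction to both numerator and denominator. SAP 12.5 writes it only for the denominator, so the liver text should state both. Show participants already above the cut-off at baseline in a separate row, so that any worsening stays visible. The other six rows can stay as they are.

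**Cost.** One baseline flag from data already collected, slightly smaller denominators in three rows, and one extra row for each.

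**SAP 12.1 and criterion 11b.** The sponsor should reconcile the Gilbert's entry allowance with the Hy's Law bilirubin component and make clear which multiple of ULN the component means. No threshold or clinical rule is proposed here.

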An additional subset of 12 participants from the Dose and Schedule Finding portion of the trial will be enrolled into the PK bridging portion of the trial at Cycle 0 to compare the systemic exposure of the RP-1664 adolescent/adult whole capsule versus a pediatric sprinkle capsule formulation.

For all participants, treatment with RP-1664 will continue until radiographic progression, intolerability to trial intervention, risk to participant as determined by the Investigator and/or Sponsor, consent withdrawal, start of a non-trial anticancer treatment, major protocol noncompliance that would jeopardize participant safety and/or data interpretation as determined by the Sponsor, pregnancy, or death. Participants are allowed to continue RP-1664 treatment after disease progression if the Investigator deems that it is in the participant's best interest. In such cases, the participant will be required to provide signed written consent agreeing to treatment after disease progression (see Section 4.1).

Eligibility Criteria

Inclusion Criteria:

To be eligible to participate in this trial, participants must meet all the following criteria:

 Written informed consent and/or assent, according to local guidelines, signed and dated by the participant or legal guardian prior to the performance of any trialspecific procedures, sampling, or analyses. Participants with impaired decision-making capacity must have a close caregiver or legally authorized representative (LAR) present.

 Male or female participants ≥ 18 years of age at the time of signing the informed consent.

US only: Male or female participants ≥ 12 years of age at the time of signing the informed consent and/or assent. Participants < 18 years of age must weigh at least 40 kg and be at a 6th grade reading level or higher, except for participants with neuroblastoma who must weigh at least 30 kg. The dose of RP-1664 will be adjusted for participants with neuroblastoma weighing 30 - < 40 kg based on the body surface area (BSA) table

Note: Participants 12 to 17 years of age will be enrolled only after at least 4 participants \geq 18 years-of-age have completed 1 cycle of therapy.

3.	Ability to comply with the	e protocol and trial procedures	

- 4. Ability to swallow and retain whole, intact oral medications.
- Life expectancy ≥ 4 months after the start of the treatment according to the Investigator's judgment.

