 - a. WOCBP is defined as fertile, following menarche and until becoming postmenopausal unless permanently sterile. WOCBP, who are sexually active, and their partners must agree to use a highly effective form of contraception throughout their participation in the trial and for 6 months after the last dose of trial intervention. Female participants must refrain from donating eggs during their participation in the trial and for 6 months following last dose of trial intervention.
 - b. Women are considered post-menopausal and not of childbearing potential if they have had no menses for 12 months without an alternative, potentially reversible medical cause or permanent sterilization methods include hysterectomy, bilateral salpingectomy, and bilateral oophorectomy. A high follicle stimulating hormone (FSH) level in the postmenopausal range may be used to confirm a postmenopausal state in women not using hormonal contraception or hormonal replacement therapy. However, in the absence of 12 months of amenorrhea, confirmation with more than one FSH measurement is required.
- 14. Male participants with female partners of childbearing potential must follow a contraception method at least as conservative as Clinical Trial Facilitation Group (CTFG) recommendations during their participation in the trial for 6 months following last dose of trial intervention. Male participants must also refrain from donating sperm during their participation in the trial and for 6 months following last dose of trial intervention.

15. For participants in the food effect portion of the trial, ability to consume a high-fat meal and fast for 12 hours.

Exclusion Criteria:

An individual who meets any of the following criteria will be excluded from participation in this trial:

- 1. History or current condition (such as transfusion-dependent anemia, thrombocytopenia, or chronic neutropenia, except for participants with neuroblastoma with bone marrow involvement) or laboratory abnormality that in the opinion of the Investigator or Sponsor might pose a significant risk to participant safety, confound the trial results, or interfere with participation for the full duration of the trial treatment.

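### Two thresholds contradict themselves: inclusion criterion 12c gives one group two ANC floors (1000 and 750), and the SAP's febrile-neutropenia DLT pairs 38.3°C with 100.4°F

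*Protocol*

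**What the plan says.** **Entry ANC.** Protocol 1.1, inclusion criterion 12c, sets a general floor of 2000 cells/mm³. It then makes an exception for neuroblastoma with bone marrow involvement, for participants "who are required to have ANC \geq 1000 cells/mm³. Participants with neuroblastoma with bone marrow involvement are required to have ANC \geq 750/uL". Both sentences name the same group. The preamble to the criteria says that "participants must meet all the following criteria".

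The neighbouring items treat this disease in two ways. 12b (hemoglobin) has one exception, for marrow involvement, and no tier for neuroblastoma without it. 12d (platelets) has both tiers: "Participants with neuroblastoma without bone marrow involvement are required to have platelet count" of at least 100,000 cells/mm³, and those with involvement need 75,000. Exclusion criterion 1 lists "chronic neutropenia, except for participants with neuroblastoma with bone marrow involvement" among its example conditions.

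**Febrile-neutropenia DLT.** SAP 12.1 reads "Febrile neutropenia (defined as absolute neutrophil count (ANC) <1000 cells" per μL, "with a single temperature of 38.3°C [100.4°F] for > 1 hour". To be a DLT the event must also be one that "is deemed at least possibly related to trial treatment, and is not clearly and incontrovertibly due to disease progression or extraneous cause". The output that uses the definition is stated as follows: "The number of DLTs will be summarized by treatment arms for the DLT Evaluable Population".

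**The concern.** These are two unrelated drafting faults, and each leaves a safety threshold with two values.

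For 12c, one site may apply 1000 and turn away a patient with ANC 800. Another may take the later sentence as the operative one and enrol that patient. This is the group in which low counts are expected, as its exemption in exclusion criterion 1 shows. The protocol also names neutropenia as an anticipated toxicity and gives it as the reason for the week off treatment.

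For the DLT, the classification of a mild fever depends on which unit is read. The phrase also joins a single reading to a duration of more than an hour, so it is unclear whether a brief reading of 38.3°C or above counts. SAP 12.1 reports DLT counts from this definition. Under SAP 6.1, having a DLT is one way into the DLT Evaluable Population, so the denominator can move as well.

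**Working it through.** **(a) ANC floors in 12c**

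1. Units: 1 mm³ = 1 μL, so the two floors are 1000 and 750 in the same unit. They differ by 1000 − 750 = 250 cells/mm³.
2. Since all criteria apply, the effective floor is max(1000, 750) = 1000. The 750 sentence then excludes nobody whom the first clause admits.
3. The disputed band is ANC 750–999: it passes the second sentence and fails the first.
4. As written, neuroblastoma *without* marrow involvement has no exception in 12c and stays at 2000. If the first clause were changed to *without*, that group's floor would fall from 2000 to 1000, which is half.

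**(b) Temperature in SAP 12.1**

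The plan's own pairing does not reproduce:

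- 38.3 × 9/5 + 32 = 100.94°F, against the stated 100.4°F.
- (100.4 − 32) × 5/9 = 38.0°C, against the stated 38.3°C.
- Rounding does not explain it: 38.25 to 38.35°C converts to 100.85 to 101.03°F.
- Gap: 38.3 − 38.0 = 0.3°C, or 100.94 − 100.4 = 0.54°F.

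The SAP gives no inequality sign; I read the figure as *at or above*. Take an event that is treatment-emergent and at least possibly related, with ANC below 1000 and not a DLT on another ground such as Grade 4 neutropenia:

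| Temperature and duration | °C figure | °F figure |
|---|---|---|
| 38.0 to <38.3°C, over 1 hour | not a DLT | DLT |
| 38.3°C or above, over 1 hour | DLT | DLT |
| 38.3°C or above, 1 hour or less | unclear | unclear |

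The third row is unclear because a single reading is tied to a duration.

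**Effect on the reported DLT summary.** SAP 6.1 counts a participant as evaluable after at least 75% of the planned Cycle 1 dose, with the required safety evaluations and observation to the end of Cycle 1, or after a DLT. With x DLTs among n evaluable participants, one reclassified event gives:

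- (x + 1)/n if the participant was already evaluable;
- (x + 1)/(n + 1) if the participant received under 75% of the planned dose and is evaluable only through the DLT.

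**The case against.** The strongest reply is that both faults are narrow. In 12c the literal reading already yields 1000. Exclusion criterion 1 still lets the investigator or sponsor exclude a laboratory abnormality judged a significant risk. Only the synopsis criteria were supplied, so the body of the protocol may be clean. For the DLT, SAP section 7 calls the analysis purely descriptive and section 13 makes no formal inference at interim evaluations, so what is shown is a possible change in a reported count. All of this stands and limits the impact, but neither contradiction goes away.

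A reader might infer more than the documents support in four places.

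- *That dose escalation is affected.* Dose decisions may rest on as few as 2 DLT-evaluable participants, so one event could weigh heavily. But the protocol's DLT section was not supplied, and it may define fever correctly.
- *That 12c simply mistypes without as with.* 12d suggests this. 12b, which is worded like the first clause of 12c, points the other way. The documents do not settle it.
- *That a participant enrolled at ANC 750–999 is half-way to a DLT before dosing.* The ANC limb would indeed be met at entry. However, SAP 12.1 and 12.2 still require the event to be treatment-emergent (new or worsened) and at least possibly related, which largely covers the case.
- *That the intended fever rule is a single reading above 38.3°C, or at least 38.0°C sustained for over an hour.* No such two-limb rule appears in the documents, and it would make brief readings above 38.3°C count as DLTs.

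**Conclusion.** Both contradictions are in the current text and should be fixed. Each document shows that its two values conflict, but not which value was intended.

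For (a), the demonstrated effect is on eligibility, and only for neuroblastoma with bone marrow involvement and ANC 750–999. For (b), it is on the classification of possibly related events with ANC below 1000, short of Grade 4 neutropenia, at 38.0 to <38.3°C for over an hour, together with unclear handling of brief readings of 38.3°C or above. Each event reclassified in (b) changes the SAP's DLT count by 1 and the DLT-evaluable denominator by 0 or 1.

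The number of participants or events in these bands cannot be estimated from the documents. The conclusion rests on the synopsis version of the criteria and on the SAP's DLT text alone.

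**What to change.** **(a) Protocol 12c.** State one ANC floor for neuroblastoma with bone marrow involvement, confirmed by the clinical team, and tell sites to apply 1000 until then. Choosing a single value for this group costs a wording correction and a notice to sites. If the sponsor wants a with/without split as in 12d, it should recognise that this lowers the floor for neuroblastoma without marrow involvement from 2000 to 1000. That is a substantive eligibility change and should be justified and processed as one.

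**(b) SAP 12.1.** Use one consistent pair, either 38.3°C [100.9°F] or 38.0°C [100.4°F]. State the inequality and whether the duration of more than 1 hour applies to it, and match the text to the protocol's DLT section, correcting that section too if it carries the same wording. A two-limb fever rule is only a suggestion for the clinical team to consider, since it would change which events are DLTs. The correction itself is a wording change with no extra participants or procedures.
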